10.2.1. Primary Endpoint

App feasibility and acceptability – that is, interest in using the app, onboarding to the app, and recommending the app to others.

10.2.1.2. Endpoint Definition for Primary Objective / Outcome

- i) Agreement to use the app
- ii) Onboarding of the app
- iii) Endorsing that they would recommend the app to others

10.2.1.3. Assessment Methods for Primary Objective / Outcome

- i) Intake interview will track the number of declines
- ii) MindCotine app will record registration
- iii) Survey

10.2.1.4. Measurement Time Points for Primary Objective / Outcome

- i) Intake interview
- ii) Intervention period
- iii) EOT

10.2.1.5. Response Review

There is no drug dosage involved. The study ends after the last participant completes their EOT assessment. Data analysis will be comparing pre- with post-treatment.

10.2.2. Secondary Endpoint(s)

Quitting, making a quit attempt during the past 6 weeks, use of cessation medications, smoking reduction (ie., change in cigarettes per day from baseline), MindCotine usage, MindCotine dropout, and adverse events.

10.3. Interim Analyses

N/A. Pilot study of N=20.

10.3.1. Stopping Rules

N/A. Pilot study of N=20.

10.4.1. Primary Analysis Population

Full sample N=20.

10.4.2. Primary Analysis Plan

Interest in using the app will be calculated as 19 out of out of the total number of patients invited to use the app minus 1.

Onboarding of the app will be calculated as the number who register with the app out of the 20 patients provided the program.

Recommending the app to others will be calculated for the N=20 participating.

10.5. Secondary Analysis

Frequency calculation of the number of participants who report being tobacco free at the end of treatment divided by the full sample size (N=20). We will assume those who drop out to be still using tobacco.

Frequency calculation of quit attempts, use of cessation medications, MindCotine dropout, and adverse events. We will calculate the mean change in reported cigarettes per day from baseline to EOT. We will calculate mean scores for MindCotine app usage.

10.5.1. Secondary Analysis Population

Full sample N=20.

10.5.2. Secondary Analysis Plan

Frequency calculation of quit attempts, use of cessation medications, MindCotine dropout, and adverse events. We will calculate the mean change in reported cigarettes per day from baseline to EOT. We will calculate mean scores for MindCotine app usage.

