3.2.2. Retention Procedures

None. After enrollment, participants will be contacted at the end of the 6-week intervention. Unless the participant reaches out to the team during the intervention period, there is no expected contact with the participant until the end of the 6-week period.

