6.2. Description of Procedures and Assessments

6.2.1. Efficacy Assessments

1. Patients who use tobacco are identified as part of the Tobacco Treatment Program. The Tobacco Treatment Specialist reaches out to these patients and offers tobacco cessation resources, and the pilot study will be offered as a part of this. Recruitment of 20 participants is estimated to take approximately 3 months.
2. If a patient expresses interest in the pilot study, they will go through a phone screen consent and questionnaire. Inclusion criteria includes daily or some day cigarette smoking, English or Spanish fluency, have compatible smartphone, willing to commit to the intervention and complete the surveys, and no history of epilepsy.

3. Informed Consent: If a patient is eligible for the study, and would like to proceed, they will go through an informed consent process provided via online link. The Tobacco Treatment Specialist will be available to go through the consent form with the patient. If signed, they will be enrolled in the pilot study, and a copy of the signed consent form can be provided via secure email or by mail.
4. Within two business days of the informed consent, a study research team will keep track of signed consents and keep track of participants, including demographics, any tobacco cessation resources the participant also wanted to use, date of screening, when the kit was mailed out, and when end of treatment will be.
5. Within two business days of the informed consent, the study team will mail out a VR kit to the participant. The VR kit should reach the participant in 3-5 business days.
6. Once the VR kit is received, the participant can have full access to the MindCotine app and start the intervention.
7. The participant interacts with the app for 6-weeks.
8. After the 6-week intervention, the study team reaches out to the participant to complete the end of treatment survey. If the team is unsuccessful with reaching the participant after 3 attempts, the participant will be considered “lost to follow up”. The end of treatment assessment will include questions on tobacco use, satisfaction with MindCotine, likelihood of recommending MindCotine to others, and whether VR side effects were experienced.
9. Any adverse effects learned of will be tracked.
10. MindCotine will provide user app data from the 20 participants.
11. The study team will link the app data to the survey data and remove identifiers.
12. [name] will conduct data analysis.

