6.2.2. Safety and Other Assessments

During screening, patients who have a history of epilepsy are not eligible for the pilot study. The VR environment may be triggering for these patients.

At end of treatment, VR side effects will be assessed.

We do not anticipate serious adverse events as a result of an app designed for smoking cessation. Should any become known to the team, [name] will be notified within 24 hours upon learning of that information, and the team will proceed according to her directions. All SAEs will be documented. [name] is a licensed clinical psychologist and has led multiple clinical trials.

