7.2.4. Time Period of Event Assessment and Follow-up

Once the participant signs the consent form, any adverse event that occurs during their study period (approx.. 6-weeks) will be kept track of once the study team learns of the event.

All possibly study related SAEs will be followed until resolution.

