4. Are you currently using any quit smoking medications?	
 a. Chantix b. Bupropion c. NRT (patches, gum, lozenges, spray) 	Original

If still smoking –
 
5. During the past 6 weeks, have you stopped smoking cigarettes for one day or longer because you were trying to quit smoking?
	
 a. Yes, stopped smoking cigarettes for one day more in an attempt to quit b. No, did not stop smoking cigarettes for one or more 	ASPiRE (modified)
6. How would you rate the MindCotine program?	
 a) Excellent b) Good c) Fair 	CSQ-8 (adapted)
7. If a friend was in need of quitting smoking, would you recommend MindCotine to them?	
 a) No, definitely not b) No, I don't think so c) Yes, I think so d) Yes, definitely 	CSQ-8 (adapted)
8. Did you experience any of the following when using the MindCotine app?	
 1. Dizziness None Mild Moderate Severe 2. Nausea None Mild Moderate Severe 3. Disorientation None Mild Moderate Severe 4. Sweating None Mild Moderate Severe 5. Headache None Mild Moderate Severe 	Original for assessing side effects of VR

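### The five VR symptoms are asked about only at end of treatment, so a frequency over the full N=20 understates them to the extent that participants do not answer or never use the app

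*Combined protocol and SAP*

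**What the plan says.** Adverse events are a secondary endpoint (Section 10.2.2). The analysis is a "Frequency calculation of quit attempts, use of cessation medications, MindCotine dropout, and adverse events" (Section 10.5.2), and the population given for it in Section 10.5.1 is "Full sample N=20".

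For the VR symptoms, Section 6.2.2 says: "At end of treatment, VR side effects will be assessed". The instrument is item 8 of the EOT survey in Section 13.2.1, which asks: "Did you experience any of the following when using the MindCotine app". It lists dizziness, nausea, disorientation, sweating and headache, each graded from none to severe.

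The checklist is planned for no other time. Section 3.2.2 states that, unless the participant makes contact, "there is no expected contact with the participant until the end of the 6-week period". Section 6.2.1 (step 8) classes a participant as lost to follow-up "If the team is unsuccessful with reaching the participant after 3 attempts".

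There is a second, unsolicited route. Under Section 7.2.4, from consent onward, "any adverse event that occurs during their study period (approx.. 6-weeks) will be kept track of once the study team learns of the event". Section 6.2.1 (step 9) and Sections 7.4 and 7.4.1 say the same in substance.

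The only missing-data rule is in Section 10.5: dropouts are taken to be still using tobacco. It applies to the quit outcome, and no rule covers a missing answer to item 8.

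**The concern.** A fixed denominator of 20 works in opposite directions for the two kinds of outcome. For quitting, keeping dropouts in the denominator as smokers is conservative. For side effects, a participant who was never asked stays in the denominator and adds to the numerator only by volunteering a report. The percentage therefore leans toward a favourable safety picture.

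Non-use has the same effect. Someone who never opened the app cannot have had a symptom while using it, but still counts among the 20. The plan allows for this, since its onboarding goal is 75% and not 100%.

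The checklist is the trial's only systematic safety measure. Its frequency should describe people who could have had the symptom and were asked about it.

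**Working it through.** **Inputs from the documents.** N = 20 (Section 10.5.1); the checklist is given once, at EOT (Sections 6.2.2 and 13.2.1); no earlier contact is planned (Section 3.2.2); the onboarding goal is 75% (Section 10.2). The plan states no expected side-effect rate, EOT response or precision, so there is no derived figure to reproduce. N = 20 is the number of kits supplied (Section 10.1.2).

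**Assumptions.** r = number answering item 8, varied; true rate 30%, for illustration; equal true risk in responders and non-responders; s = share of non-responders' symptoms that reach the team spontaneously.

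**Step 1: shrinkage from non-response.** If non-responders with no report add nothing to the numerator:

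reported rate / true rate = [r + (20 − r)s] / 20

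| r | Factor, s = 0 | True 30% reported as | Factor, s = 0.5 | True 30% reported as |
|---|---|---|---|---|
| 20 | 1.00 | 30% | 1.00 | 30% |
| 18 | 0.90 | 27% | 0.95 | 28.5% |
| 14 | 0.70 | 21% | 0.85 | 25.5% |
| 10 | 0.50 | 15% | 0.75 | 22.5% |

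**Step 2: shrinkage from non-use.** If exactly 75% register, 15 of 20 could have been exposed. Even with complete EOT response, a 30% rate among users becomes 0.30 × 15/20 = 22.5% over 20.

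**Step 3: what the alternative looks like.** Take x = 5 participants reporting a symptom, with exact (Clopper-Pearson) 95% intervals. The bounds run from x/20 (no one with unknown status had it) to (x + 20 − r)/20 (all of them did).

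| r | x/20 | x/r | Bounds over 20 |
|---|---|---|---|
| 18 | 25.0% (8.7–49.1) | 27.8% (9.7–53.5) | 5/20 to 7/20 = 25–35% |
| 14 | 25.0% (8.7–49.1) | 35.7% (12.8–64.9) | 5/20 to 11/20 = 25–55% |

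The x/20 column is the same in both rows and so does not show how much is unknown.

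**Step 4: no events.** The two-sided 95% upper limit for zero events is 16.8% at n = 20, 18.5% at n = 18, 23.2% at n = 14 and 30.8% at n = 10. Quoting the n = 20 limit when 14 people answered claims more reassurance than the data give.

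**The case against.** A reader might infer that every non-responder is counted as event-free and that VR side effects are therefore understated. The documents do not support that.

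- **No such rule is written.** Section 10.5.1 names a population, and the plan is silent on missing item 8 answers. The explicit division by 20 and the dropout rule in Section 10.5 belong to the quit rate.
- **Adverse events have another route.** Events learned of outside the survey are tracked from consent, and participants may contact the team at any time (Section 4.1.4.4). A non-responder with a known event would be counted. For such events, all 20 enrolled is a reasonable denominator.
- **The understatement is conditional.** It needs non-response or non-use. The earlier pilot cited in Section 1.2.3 had follow-up above 90%. At that level the non-response shortfall is under 10% in relative terms, or less than 3 points on a true 30%, which is small in a descriptive pilot of 20.

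Two further inferences also go too far. Section 5.7 lets a participant with VR sickness take off the headset, but nothing links this to failing to answer the survey. Nor do the documents show that the side-effect rate drives adoption: Section 2.1.4 lists interest, onboarding, recommendation, reduction and quitting, with no safety threshold.

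These points limit the concern to the five solicited symptoms without removing it. The unsolicited route depends on participants volunteering information, and with half of non-responders' symptoms volunteered the factor at 14 responders is still 0.85. The follow-up in the earlier pilot is not an assumption of this trial, which plans no retention procedures.

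**Conclusion.** The concern holds for the EOT symptom checklist and not for adverse events in general. Read as written, Sections 10.5.1 and 10.5.2 divide checklist symptoms by 20 whatever the number asked, with no rule for missing answers.

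With equal risk and no spontaneous reports, the rate shrinks by r/20, so a true 30% becomes 27%, 21% or 15% with 18, 14 or 10 responders. Spontaneous reports lessen the loss, non-use of the app adds to it, and at 20 of 20 responding there is none from non-response. The size rests on assumed response counts and an assumed true rate. The primary feasibility endpoints are unaffected. The change is worth making because a better denominator is available from data already being collected.

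**What to change.** In Sections 10.5.1 and 10.5.2:

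1. Report each checklist symptom among participants who answered EOT item 8, and show beside it how many registered with the app. Registration is already recorded (Section 10.2.1.3). It is only an upper limit on VR exposure, because the program also has 2D and audio content (Section 1.2.2).
2. State how many of the 20 have unknown symptom status, and give x/20 to (x + number unknown)/20 as labelled bounds.
3. Report all known AEs and SAEs separately over all 20 enrolled. They should not be restricted to registered EOT responders, since that would drop known events in people who were later lost.

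This takes a few sentences and no new data. The cost is slightly higher percentages and wider intervals.

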10.5.3. Sample Size

N=20.

10.5.4. Accrual estimates

4 patients a month.

10.5.4.1. Sample size justification

Initial pilot to examine feasibility and acceptability.

10.5.4.2. Effect size justification

N/A. This pilot study is not powered to test efficacy.

10.5.4.3. Criteria for future studies

If found to be feasible to deliver and acceptable among our patient population, we will consider a larger evaluation powered to test efficacy.

10.6. Descriptive Statistics and Exploratory Data Analysis

Per responses above, this pilot study is descriptive in nature.

12. PROTOCOL HISTORY

Amendment (version) Date *	Change Summary
1 (9.7.21)	Updated to respond to tabled comments.

* Latest version date should match footer date of the current protocol

13. APPENDICES

13.1. Appendix A. References for Stanford Cancer Institute Policies & Practices

Relevant Stanford Cancer Institute (SCI) process, policies, and documentation include the following.

Standard Operating Procedures (SOPs):

- Stanford School of Medicine standard operating procedure SOP-005 “Identifying and Reporting Adverse Events.” This document is available on the Spectrum website.
http://med.stanford.edu/spectrum/b4_research_quality/b4_3_standard_operating_procedures.html.
- SCI Scientific Review Committee (SRC) Policies and Procedures
http://med.stanford.edu/content/dam/sm/cancer/documents/PRMSDocuments/SRC_SOP.pdf.
- SCI Institutional Data and Safety Monitoring Plan.
<http://med.stanford.edu/cancer/research/trial-support/dsmc.html>.
- SCI Data Management in Clinical Investigations
http://med.stanford.edu/content/dam/sm/ccto/sunet_id_resources/regulatory_documents/sop/SOP-Data%20Management.pdf.

Logs and Forms:

- The SCI Adverse Event Log (editable):
http://med.stanford.edu/content/dam/sm/ccto/sunet_id_resources/coordinator_documents/Adverse%20Event%20Log.pdf.
- SCI Serious Adverse Event Report Form (editable):
http://med.stanford.edu/content/dam/sm/ccto/sunet_id_resources/coordinator_documents/SAE_CRF.pdf.
- Sample Study Participant Log (editable):
http://med.stanford.edu/content/dam/sm/ccto/sunet_id_resources/coordinator_documents/Subject_Log_07.29.11.doc.

Guidelines:

Current Stanford University IRB policies and procedures:

- Stanford University Human Research Protection Program (HRPP) Policy Manual at:
http://researchcompliance.stanford.edu/hs/hrpp/Documents/hrpp_entire.pdf.
- Stanford University HRPP Policy Guidance Events and Information that Require Prompt Reporting to the IRB GUI-P13 at:
http://humansubjects.stanford.edu/research/documents/Events-Info-Report-to-IRB_GUI03P13.pdf.

- Stanford University HRPP Unanticipated Problem reporting process is defined at Section 3.10, in the Human Research Protection Program (HRPP) Policy Manual http://researchcompliance.stanford.edu/hs/hrpp/Documents/hrpp_entire.pdf.

Other regulatory documentation and resources

- The Common Terminology Criteria for Adverse Events (CTCAE) **version 5** are available at: https://ctep.cancer.gov/protocoldevelopment/electronic_applications/ctc.htm#ctc_50, see https://ctep.cancer.gov/protocoldevelopment/electronic_applications/docs/CTCAE_v5.0.xlsx OR https://ctep.cancer.gov/protocolDevelopment/electronic_applications/docs/CTCAE_v5_Quick_Reference_8.5x11.pdf.
- The International Conference on Harmonization (ICH) Guideline on Good Clinical Practice (ICH GCP E6r1), including adverse event reporting, is available at: http://www.ich.org/fileadmin/Public_Web_Site/ICH_Products/Guidelines/Efficacy/E6/E6_R1_Guideline.pdf.

These links may change from time to time, and will be updated in this template as needed. Consult issuing authority as needed.

13.2. Appendix B. Other appendices as needed

13.2.1 Questionnaires

Screening section:

3. How many cigarettes did you smoke in the past 7 days?
 
If 0, 1, 2, 3, 4, 5, 6, 7, 8, 9, 10, 11, 12, 13, 14, 15, 16, 17, 18, 19, 20, 21, 22, 23, 24, 25, 26, 27, 28, 29, 30, 31, 32, 33, 34, 35, 36, 37, 38, 39, 40, 41, 42, 43, 44, 45, 46, 47, 48, 49, 50, 51, 52, 53, 54, 55, 56, 57, 58, 59, 60, 61, 62, 63, 64, 65, 66, 67, 68, 69, 70, 71, 72, 73, 74, 75, 76, 77, 78, 79, 80, 81, 82, 83, 84, 85, 86, 87, 88, 89, 90, 91, 92, 93, 94, 95, 96, 97, 98, 99, 100, 101, 102, 103, 104, 105, 106, 107, 108, 109, 110, 111, 112, 113, 114, 115, 116, 117, 118, 119, 120, 121, 122, 123, 124, 125, 126, 127, 128, 129, 130, 131, 132, 133, 134, 135, 136, 137, 138, 139, 140, 141, 142, 143, 144, 145, 146, 147, 148, 149, 150, 151, 152, 153, 154, 155, 156, 157, 158, 159, 160, 161, 162, 163, 164, 165, 166, 167, 168, 169, 170, 171, 172, 173, 174, 175, 176, 177, 178, 179, 180, 181, 182, 183, 184, 185, 186, 187, 188, 189, 190, 191, 192, 193, 194, 195, 196, 197, 198, 199, 200, 201, 202, 203, 204, 205, 206, 207, 208, 209, 210, 211, 212, 213, 214, 215, 216, 217, 218, 219, 220, 221, 222, 223, 224, 225, 226, 227, 228, 229, 230, 231, 232, 233, 234, 235, 236, 237, 238, 239, 240, 241, 242, 243, 244, 245, 246, 247, 248, 249, 250, 251, 252, 253, 254, 255, 256, 257, 258, 259, 260, 261, 262, 263, 264, 265, 266, 267, 268, 269, 270, 271, 272, 273, 274, 275, 276, 277, 278, 279, 280, 281, 282, 283, 284, 285, 286, 287, 288, 289, 290, 291, 292, 293, 294, 295, 296, 297, 298, 299, 300, 301, 302, 303, 304, 305, 306, 307, 308, 309, 310, 311, 312, 313, 314, 315, 316, 317, 318, 319, 320, 321, 322, 323, 324, 325, 326, 327, 328, 329, 330, 331, 332, 333, 334, 335, 336, 337, 338, 339, 340, 341, 342, 343, 344, 345, 346, 347, 348, 349, 350, 351, 352, 353, 354, 355, 356, 357, 358, 359, 360, 361, 362, 363, 364, 365, 366, 367, 368, 369, 370, 371, 372, 373, 374, 375, 376, 377, 378, 379, 380, 381, 382, 383, 384, 385, 386, 387, 388, 389, 390, 391, 392, 393, 394, 395, 396, 397, 398, 399, 400, 401, 402, 403, 404, 405, 406, 407, 408, 409, 410, 411, 412, 413, 414, 415, 416, 417, 418, 419, 420, 421, 422, 423, 424, 425, 426, 427, 428, 429, 430, 431, 432, 433, 434, 435, 436, 437, 438, 439, 440, 441, 442, 443, 444, 445, 446, 447, 448, 449, 450, 451, 452, 453, 454, 455, 456, 457, 458, 459, 460, 461, 462, 463, 464, 465, 466, 467, 468, 469, 470, 471, 472, 473, 474, 475, 476, 477, 478, 479, 480, 481, 482, 483, 484, 485, 486, 487, 488, 489, 490, 491, 492, 493, 494, 495, 496, 497, 498, 499, 500, 501, 502, 503, 504, 505, 506, 507, 508, 509, 510, 511, 512, 513, 514, 515, 516, 517, 518, 519, 520, 521, 522, 523, 524, 525, 526, 527, 528, 529, 530, 531, 532, 533, 534, 535, 536, 537, 538, 539, 540, 541, 542, 543, 544, 545, 546, 547, 548, 549, 550, 551, 552, 553, 554, 555, 556, 557, 558, 559, 560, 561, 562, 563, 564, 565, 566, 567, 568, 569, 570, 571, 572, 573, 574, 575, 576, 577, 578, 579, 580, 581, 582, 583, 584, 585, 586, 587, 588, 589, 590, 591, 592, 593, 594, 595, 596, 597, 598, 599, 600, 601, 602, 603, 604, 605, 606, 607, 608, 609, 610, 611, 612, 613, 614, 615, 616, 617, 618, 619, 620, 621, 622, 623, 624, 625, 626, 627, 628, 629, 630, 631, 632, 633, 634, 635, 636, 637, 638, 639, 640, 641, 642, 643, 644, 645, 646, 647, 648, 649, 650, 651, 652, 653, 654, 655, 656, 657, 658, 659, 660, 661, 662, 663, 664, 665, 666, 667, 668, 669, 670, 671, 672, 673, 674, 675, 676, 677, 678, 679, 680, 681, 682, 683, 684, 685, 686, 687, 688, 689, 690, 691, 692, 693, 694, 695, 696, 697, 698, 699, 700, 701, 702, 703, 704, 705, 706, 707, 708, 709, 710, 711, 712, 713, 714, 715, 716, 717, 718, 719, 720, 721, 722, 723, 724, 725, 726, 727, 728, 729, 730, 731, 732, 733, 734, 735, 736, 737, 738, 739, 740, 741, 742, 743, 744, 745, 746, 747, 748, 749, 750, 751, 752, 753, 754, 755, 756, 757, 758, 759, 760, 761, 762, 763, 764, 765, 766, 767, 768, 769, 770, 771, 772, 773, 774, 775, 776, 777, 778, 779, 780, 781, 782, 783, 784, 785, 786, 787, 788, 789, 790, 791, 792, 793, 794, 795, 796, 797, 798, 799, 800, 801, 802, 803, 804, 805, 806, 807, 808, 809, 810, 811, 812, 813, 814, 815, 816, 817, 818, 819, 820, 821, 822, 823, 824, 825, 826, 827, 828, 829, 830, 831, 832, 833, 834, 835, 836, 837, 838, 839, 840, 841, 842, 843, 844, 845, 846, 847, 848, 849, 850, 851, 852, 853, 854, 855, 856, 857, 858, 859, 860, 861, 862, 863, 864, 865, 866, 867, 868, 869, 870, 871, 872, 873, 874, 875, 876, 877, 878, 879, 880, 881, 882, 883, 884, 885, 886, 887, 888, 889, 890, 891, 892, 893, 894, 895, 896, 897, 898, 899, 900, 901, 902, 903, 904, 905, 906, 907, 908, 909, 910, 911, 912, 913, 914, 915, 916, 917, 918, 919, 920, 921, 922, 923, 924, 925, 926, 927, 928, 929, 930, 931, 932, 933, 934, 935, 936, 937, 938, 939, 940, 941, 942, 943, 944, 945, 946, 947, 948, 949, 950, 951, 952, 953, 954, 955, 956, 957, 958, 959, 960, 961, 962, 963, 964, 965, 966, 967, 968, 969, 970, 971, 972, 973, 974, 975, 976, 977, 978, 979, 980, 981, 982, 983, 984, 985, 986, 987, 988, 989, 990, 991, 992, 993, 994, 995, 996, 997, 998, 999, 1000
	_____	standard

4. Are you currently using any other tobacco products? (select all that apply)
	
 a. E-cigarettes/vaping devices b. Non-tobacco nicotine products (e.g. Zyn) c. Cigars, cigarillos, little filtered cigars d. Heated tobacco (IQOS) e. Blunts f. None 	original question

6. Do you use a smartphone?
 
If No, pt is not eligible.
	
 a. Yes b. No 	original

7. What smartphone device and version do you use?
 
If a or c is selected, pt not eligible. Phone is not compatible.
 
If e is selected, check with MindCotine on compatibility if they do not screen out in later questions.
	
 a. Older than iPhone 4 b. iPhone 4 or newer c. Older than Android version 4.1 d. Android version 4.1 or newer e. Other/Unknown 	original

8. Would you be available to interact with a smartphone app for a 6 week period?
 
If No, pt is not eligible.
	
a. Yes b. No
	
iginal

9. Would you be available to answer questions about the program at the end of the 6 week period?
 
If No, pt is not eligible.
	
a. Yes b. No
	
iginal

Thank you for your responses. Unfortunately it does not look like this treatment option is a good fit for you. We are happy to share other treatment options available to you.
 
If patient asks why, can explain: The treatment option... [Q1] is offered for current cigarette smokers. [Q3] is offered to those who smoke more frequently. This is so we can better understand if the intervention is useful. [Q5] is not designed in other languages. [Q6, Q7] works on newer smartphones. [Q8, Q9] is being tried out with a limited amount of patients to see whether it is an option worth offering to our patients in the future and for this to work out, we would like
	
reen out
	

Thank you for your responses.
 
[for staff] Go through phone consent. Then set up with intervention if consent is obtained.
	
reen in
	

[for staff] After screen in, keep track of patient, their start date, demographics, and do end of treatment when it's time.

End of Treatment:

3. Are you currently using any other tobacco or nicotine products? (select all that apply)	
 a. E-cigarettes/vaping devices b. Non-tobacco nicotine products (e.g. Zyn) c. Cigars, cigarillos, little filtered cigars d. Heated tobacco (IQOS) e. Blunts 	Original
4. Are you currently using any quit smoking medications?	
 a. Chantix b. Bupropion c. NRT (patches, gum, lozenges, spray) 	Original

If still smoking –
 
5. During the past 6 weeks, have you stopped smoking cigarettes for one day or longer because you were trying to quit smoking?
	
 a. Yes, stopped smoking cigarettes for one day more in an attempt to quit b. No, did not stop smoking cigarettes for one or more 	ASPiRE (modified)
6. How would you rate the MindCotine program?	
 a) Excellent b) Good c) Fair 	CSQ-8 (adapted)
7. If a friend was in need of quitting smoking, would you recommend MindCotine to them?	
 a) No, definitely not b) No, I don't think so c) Yes, I think so d) Yes, definitely 	CSQ-8 (adapted)
8. Did you experience any of the following when using the MindCotine app?	
 1. Dizziness None Mild Moderate Severe 2. Nausea None Mild Moderate Severe 3. Disorientation None Mild Moderate Severe 4. Sweating None Mild Moderate Severe 5. Headache None Mild Moderate Severe 	Original for assessing side effects of VR

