5.4. Treatment Duration

The intervention period is 6-weeks. Estimated participation of 10 min per day interacting with the program.

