6. STUDY PROCEDURES AND ASSESSMENTS

6.1. Schedule of Events

Schedule of Events

	screening			Wk 3		Wk 5			Wk 8		Wk 10	Wk 11
Phone consent	X											
Smartphone compatibility	X											
TTS cessation services	X											
Notes	Ideally the EOT survey is completed as close as possible to 6-weeks. It's possible the study team will tempt follow up for up to three times after the intervention period.											
Recruitment			X		X			X		X		

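### The quit-attempt window is counted back from the day the survey is answered, so for a late responder it may leave out early treatment weeks and take in weeks after treatment

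*Combined protocol and SAP*

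**What the plan says.** The End of Treatment questionnaire in Section 13.2.1 asks about quit attempts in item 5. It is put only to those to whom "If still smoking" applies, it opens "During the past 6 weeks, have you", and the affirmative answer reads "Yes, stopped smoking cigarettes for one day more in an attempt to quit". As shown, it takes yes or no and collects no date of attempt.

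Section 10.2.2 lists the endpoint as "making a quit attempt during the past 6 weeks", and the synopsis has the same look-back. Sections 10.5 and 10.5.2 analyse it as a simple frequency, and Section 10.5.1 gives the population as the full sample of 20. No rule covers surveys answered late.

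On timing, Section 5.4 states "The intervention period is 6-weeks". The notes to the Schedule of Events (Section 6.1) say "Ideally the EOT survey is completed as close as possible to 6-weeks", and Section 5.10 says only that the survey follows soon after treatment. Section 6.2.1, step 8, defines loss to follow-up by number of contacts rather than elapsed time: "If the team is unsuccessful with reaching the participant after 3 attempts". Section 3.2.2 expects no contact with participants before the 6 weeks are over.

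The start of the 6 weeks is described in two ways. Section 5.10 places the end of treatment six weeks after enrollment. Section 6.2.1, steps 6 and 7, has the intervention begin once the kit has arrived.

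**The concern.** A 6-week look-back on an end-of-treatment form, after a 6-week intervention, is most naturally read as meant to cover the intervention. It does so only if the survey is answered on the last day of treatment. After that, the window moves forward with the survey date, so participants reached at different times report on different parts of treatment.

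Those affected are the participants who are hard to reach. Attempts made soon after the kit arrives are the ones that drop out of the window. Item 5 is the only legible source for this endpoint, and without an attempt date in it, a misplaced attempt cannot be identified from the answer itself.

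**Working it through.** The plan states no figure for this endpoint, so there is none to reproduce. The check is an overlap of two intervals.

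**Inputs**
- Treatment length: 42 days (Section 5.4).
- Look-back: 42 days before the survey (item 5; Section 10.2.2).
- Sample: 20 (Section 10.5.1).
- Kit delivery: mailed within two business days of consent, then 3 to 5 business days in transit (Section 6.2.1, step 5).
- Delay *d* from end of treatment to survey: not in the documents. Assumed range 0 to 42 days.

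**Step 1: the 6 weeks run from app start.** Treatment is day 0 to day 42 and the survey is on day 42 + *d*, so the item covers day *d* to day 42 + *d*.
- Treatment days covered = max(0, 42 − *d*)
- Share of treatment omitted = *d*/42, for *d* up to 42
- Post-treatment days included = min(*d*, 42)

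| Delay *d* (days) | Treatment days covered | Share omitted | Post-treatment days included |
|---|---|---|---|
| 0 | 42 | 0% | 0 |
| 3 | 39 | 7.1% | 3 |
| 7 | 35 | 16.7% | 7 |
| 14 | 28 | 33.3% | 14 |
| 21 | 21 | 50.0% | 21 |
| 42 | 0 | 100% | 42 |

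**Step 2: when the answer is wrong for the treatment period.**
- A false no requires that every attempt made during treatment lies wholly in the first *d* days and that no later attempt falls in the window.
- A false yes requires that the only attempt in the window came after day 42 and that the participant had relapsed by the survey, because only those still smoking are asked.

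**Step 3: three example records, counted from app start, all smoking at the survey.**
- Attempt in week 4, survey at the end of week 6: the window is weeks 0 to 6. Scored yes, correctly.
- Single one-day attempt in week 1, survey at the end of week 8: the window is weeks 2 to 8. Scored no, although the attempt was made during treatment.
- First attempt in week 7, survey at the end of week 8: the window is weeks 2 to 8. Scored yes, although no attempt was made during treatment.

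**Step 4: weight of one error.** 1/20 = 5 percentage points.

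**Step 5: the 6 weeks run from enrollment (Section 5.10).** Take enrollment as the weekday of consent. Let the kit arrive *L* calendar days later and the survey be answered on day 42 + *e*.
- App-access days lost at the start = max(0, *e* − *L*)
- Days before the kit arrived that are included = max(0, *L* − *e*)

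Delivery takes between 3 business days (posted at once, fastest transit) and 7 (2 + 5). Allowing for weekends, that is 3 to 5 calendar days at the short end and 9 to 11 at the long end. Five business days is 7 calendar days.
- *L* = 7, *e* = 0: the on-time survey includes 7 days before the kit arrived.
- *L* = 7, *e* = 7: no app-access days are lost.
- *L* = 3, *e* = 7: 4 app-access days are lost.

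So the 16.7% at a one-week delay applies to the app-start clock and not to this one.

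**The case against.** The strongest reply is that item and endpoint agree. Both look back six weeks from the survey, so the item measures what Section 10.2.2 names. That stands. A reader might infer that the questionnaire contradicts the endpoint, but it does not: one unanchored window appears in both places. The example records are wrong only against the treatment period, and that this was the intended target is an inference, though a reasonable one. The synopsis also lets participants use the app for up to a year, so an attempt in week 7 may still have been made with its help.

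A reader might also infer that any late responder with an early attempt is scored no, or that the reported frequency must be too low. The documents support neither. Misclassification needs the conditions in Step 2. The window stays 42 days long at any delay, so gains and losses may offset each other unless attempts cluster early. The documents give neither the timing of attempts nor the delays. A modelled bias would rest wholly on assumed rates and would also have to allow for the restriction to those still smoking.

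Nor can it be said that the data could never be repaired. End of Treatment items 1 and 2 and much of the schedule table are not legible in the available copy and may bear on timing. Participants can also set a quit date in the app (Section 1.2.2). A chosen date is not a day of abstinence, however, and no section names it as a source for this endpoint.

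Finally, delays may be short, as the plan intends. That limits the size of the problem. It does not supply a latest date.

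**Conclusion.** The point holds as a cheap improvement to one descriptive secondary endpoint. As written, the window depends on when the participant happens to be reached, and nothing legible limits how late that may be.

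Counted from app start, the omitted share of treatment is 17%, 33% and 50% at delays of 1, 2 and 3 weeks, per late responder, and zero for an on-time survey. If the 6 weeks run from enrollment, a delay shorter than the delivery time loses no app access, but even an on-time survey reaches back before the kit arrived. The start of the 6 weeks therefore has to be settled first.

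The net direction and size of error in the reported frequency cannot be derived from the documents. Quit attempts carry no target in Section 10.2 and do not enter the feasibility metrics or the quit rate. Who is asked item 5 is a separate matter: the window would still move with the survey date if everyone were asked.

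**What to change.** 1. Reconcile Section 5.10 (six weeks from enrollment) with Section 6.2.1, steps 6 and 7 (from kit arrival), so that the period has one stated start.
2. In item 5, replace the opening look-back with *Between [recorded start date] and [date 6 weeks later], did you…* and keep the rest of the question. Staff fill in the dates. The staff note in Section 13.2.1 already calls for the start date to be tracked, and Section 10.2.1.3 says the app records registration; either could supply the date once step 1 is done. The tracker in Section 6.2.1, step 4, is said to hold the mail-out and planned end-of-treatment dates but not kit receipt, so the wording should not depend on a receipt date.
3. In the synopsis and Section 10.2.2, change the endpoint's time frame to *during the 6-week intervention period*.
4. Record the date each survey is answered, so that the actual delays can be reported.

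With the dates fixed, the item covers all 42 treatment days and no later ones at any delay. The cost is one reworded item, two endpoint phrases, one recorded date, the clarification in step 1 and an IRB modification. Late responders must recall a slightly more distant period, and the item moves further from its source, which the questionnaire already marks as modified.
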